### 5.9.5. Vital Signs

Vital signs include systolic and diastolic blood pressures, heart rate, respiratory rate, and body temperature. Supine blood pressure and heart rate measurements will be obtained after at least 3 minutes of rest.

At specified time points (see [Schedule of Assessments](#)), the supine measurements will be followed by measurements in the standing position (after standing for at least 3 minutes) to allow for orthostatic assessments. Orthostatic hypotension is defined as symptomatic orthostatic dizziness or a decrease of  $\geq 20$  mmHg in systolic blood pressure upon standing compared with the average of the resting blood pressure measurement.

Descriptive summaries of vital signs (body temperature, respiratory rate, systolic blood pressure, diastolic blood pressure, and heart rate; including orthostatic change) and their change from baseline/period-baseline will be presented by visit/study day, time point, position (as applicable), and treatment.

The following out-of-range vital signs will be summarized for analysis records occurring post-baseline:

- Heart Rate – Supine
  - <45 bpm
  - <60 bpm
  - >100 bpm
- Systolic Blood Pressure- Supine
  - $\leq 90$  mmHg
  - $\geq 140$  mmHg
- Diastolic Blood Pressure- Supine
  - $\leq 60$  mmHg
  - $\geq 90$  mmHg
- Respiratory Rate
  - <10 bpm
  - <12 bpm
  - >20 bpm
- Temperature
  - $<35.3^{\circ}\text{C}$
  - $>37.7^{\circ}\text{C}$

Vital sign results, including orthostatic changes, will be listed. An additional listing of out-of-range vital signs will also be listed.

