7.	Use of prohibited medication prior to randomization or likely to require prohibited concomitant therapy (eg, prescription and over-the-counter medications, herbal medications, vitamins, and supplements) during the trial (see Section 6.5).	
Laboratory 7	Test Results	
8.	Either of the following: • History of HIV, hepatitis B, or hepatitis C infection	
	 Positive result for HIV, hepatitis B surface antigen, hepatitis B core antibody, or hepatitis C antibody 	
9.	Positive drug screen (including nicotine) or a positive test for alcohol (note: individuals who test positive for nicotine or alcohol may be rescreened).	
10.	Any of the following clinical laboratory test results (and confirmed by a single repeat measurement, if deemed necessary):	
	• AST or ALT ≥1.5 × ULN	
	 Total bilirubin ≥1.5 × ULN. Individuals with a history or suspicion of Gilbert's syndrome may be eligible provided the direct bilirubin is <uln.< li=""> </uln.<>	

11.	Estimated glomerular filtration rate at Screening <90 mL/min/1.73 m2, as calculated using the Chronic Kidney Disease Epidemiology Collaboration (CKD-EPI) equation (Levey et al, 2009).	
Other Exclusion	onary Assessments	
12.	12-lead ECG demonstrating any of the following at Screening or initial Check-in (Day -1): • QTcF interval >450 ms • QRS interval >120 ms • PR interval >220 ms Note: at Screening, eligibility will be determined based on the average of a centrally read triplicate set of ECGs. At initial Check-in (Day -1), a single ECG will be obtained. If any of the above criteria are not met at subsequent Check-ins, consult the medical monitor to determine whether the participant remains eligible to continue in the trial.	
13.	Blood pressure measurements demonstrating any of the following at Screening or Check-in (Day -1 of each period): • Systolic blood pressure ≥140 mmHg or diastolic blood pressure ≥90 mmHg • Blood pressure will be measured after at least 3 minutes in supine position. At Screening, the average of 2 measurements will be used to determine eligibility and a single measurement at each Check-in. • Orthostatic hypotension, defined as a decrease of ≥20 mmHg in systolic blood pressure upon standing compared with the supine blood pressure measurement (at Screening, relative to the average measurement) • Symptomatic orthostatic dizziness	

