14.	Heart rate <45 bpm or >100 bpm based on vital signs assessment (rather than ECG). Heart rate will be measured in a supine position after at least 3 minutes of rest. The average of 2 measurements taken 1-2 minutes apart will be used to determine eligibility at Screening and a single measurement at each Check-in.	
15.	Any other abnormal safety findings unless, based on the investigator's judgment, the findings are not medically significant and would not impact the safety of the participant or the interpretation of the trial results. The medical monitor should be contacted to discuss individual cases, as needed. Tests with abnormal results may be repeated to ensure the reproducibility of the result before excluding a potential participant based on criteria provided in the protocol.	
Lifestyle or Ot	her Miscellaneous Exclusions	
16.	Refusal to abstain from grapefruit-containing foods or beverages or Seville orange-containing foods or beverages from 7 days prior to Day -1 through Check-out from the clinic for each treatment period.	
17.	Current use of tobacco or nicotine-containing products (cigarettes, cigars, chewing tobacco, snuff, e-cigarettes, etc).	
18.	History of chronic consumption of >400 mg/day of caffeine-containing drinks or food (eg, >4 cups [8 ounces] of brewed coffee, 9 cans [12 oz] of diet cola, 12 cans [12 oz] of cola, 8.5 cups of brewed black tea, 2 energy shot drinks).	
19.	Refusal to adhere to lifestyle considerations as defined in Section 5.3.	
20.	Considering or scheduled to undergo any surgical procedure during the trial.	
	Any other condition that would preclude IMP administration or trial participation (eg, difficulty swallowing, poor venous access).	

22.	Known allergy or hypersensitivity to the IMP, closely related compounds, or any of their specified ingredients.
23.	Donated more than 500 mL of blood in the 2 months prior to signing the ICF.
24.	Current enrollment or past participation within 30 days or 5 half-lives (whichever is longer) prior to signing the ICF in any other clinical trial involving an IMP.
25.	Employee of the investigator, clinic, or sponsor with direct involvement in the proposed trial or other trials under the direction of the investigator or clinic, as well as family members of the employee or investigator.
26.	Anyone who should not participate in the trial in the opinion of the sponsor, investigator, or medical monitor.
27.	Part B only: anyone who participated in Part A of the trial.

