### **Orthostatic Vital Sign Change**

Orthostatic change for blood pressure and heart rate is calculated as the difference in the standing value from the supine value (ie, supine value – standing value) both collected at the same visit, date, and timepoint.

The image consists of several large, solid black rectangular blocks of varying sizes. These blocks are arranged in a way that suggests a layered or overlapping effect. The most prominent block is a large rectangle at the top, with a smaller one nested within its lower right corner. Below these, there is a large horizontal rectangle in the center, flanked by two smaller vertical rectangles on the left. In the bottom right corner, there is a small, isolated white shape that resembles a stylized 'T' or a cross. The overall composition is abstract and minimalist, using only black and white colors and geometric shapes.

[REDACTED]

[REDACTED]

[REDACTED]

[REDACTED]

[REDACTED]

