## **4.2. Visit Windows**

### **4.2.1. Method of Aligning Measurements to Treatment for Part A (SAD)**

Given the crossover nature of Part A, measurements will be assigned to treatment based on treatment received at each analysis period. The start of a given analysis period will be defined as the time in which a subject takes the first dose of IMP for that analysis period. The end of the

analysis period will be the last measurement taken prior to the start of the next analysis period or the end of the study.

Measurements taken on or after the initiation of IMP in Period 1, and before dosing with IMP for Period 2, or through the end of the study if Period 2 dosing is not initiated, are considered Period 1 measurements, and will be assigned to the treatment randomized or received in Period 1, as appropriate. Measurements taken on or after the initiation of IMP in Period 2, and before dosing with IMP for Period 3, or through the end of the study if Period 3 dosing is not initiated, are considered Period 2 measurements, and will be assigned to the treatment randomized or received in Period 2, as appropriate. Measurements taken on or after the initiation of IMP in Period 3, and before dosing with IMP for Period 4, or through the end of the study if Period 4 dosing is not initiated, are considered Period 3 measurements, and will be assigned to the treatment randomized or received in Period 3, as appropriate. A measurement taken after initiation of dosing for Period 4 is considered a Period 4 event and is assigned to the treatment randomized or received in Period 4, as appropriate.

The 12-lead ECG and vital sign measurements performed pre-dose on Day 1 of each period will serve as the period-specific baseline. For safety laboratory tests, C-SSRS, and vital sign measurements (standing heart rate and blood pressure) not performed pre-dose on Day 1, the assessment performed on the check-in day (Day -1) for each period serves as the baseline value for that period. For [REDACTED] the Predose value for a specific period will serve as the Period Baseline. [REDACTED]

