#### 5.9.4. Clinical Laboratory Assessments

Descriptive summaries of selected (quantitative) clinical laboratory results will be presented by study day and treatment group. Laboratory values outside the normal range for each parameter will be identified using shift tables. Each subject's hematology, blood chemistry, and quantitative urinalysis values will be flagged as "low" (below the lower limit of normal/LLN), "normal" (within the normal range), or "high" (above the upper limit of normal/ULN) relative to the normal ranges of the central laboratory. Each subject's qualitative urinalysis values will be flagged as "normal" or "abnormal". Shifts from baseline, or period baseline if Part A, to high/normal/low status for hematology and blood chemistry parameters that are not CTCAE graded will be presented to the maximum post-baseline/post-period baseline value and the minimum post-baseline/post-period baseline value for each laboratory test. Shifts from baseline, or period baseline if Part A, to normal/abnormal status for urinalysis parameters that are not CTCAE graded will be presented to the maximum post-baseline/post-period baseline value and the minimum post-baseline/post-period baseline value for each laboratory test. Otherwise, for hematology, blood chemistry, and urinalysis parameters that are CTCAE graded, laboratory toxicities will be programmatically graded by severity using Cerevel's modified CTCAE Version 5.0. Shifts from baseline, or period baseline if Part A, to greatest (worst) treatment-emergent laboratory toxicity will be presented.

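### The out-of-range vital-sign table in SAP 5.9.5 has no baseline or change condition, so limits that eligibility does not exclude can carry a sizeable drug-free background

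*SAP*

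**What the plan says.** SAP 5.9.5 (Vital Signs) has two tabulations. The first is descriptive: vital signs and "their change from baseline/period-baseline will be presented by visit/study day, time point, position (as applicable), and treatment". The second is the abnormal-value table: "The following out-of-range vital signs will be summarized for analysis records occurring post-baseline". It lists twelve fixed limits, among them supine heart rate <45, <60 and >100 bpm, supine systolic <=90 and >=140 mmHg, and supine diastolic <=60 and >=90 mmHg. No baseline value or change enters this second rule. The section also does not say whether participants or records are counted.

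Eligibility is set in Protocol 5.2. Criterion 14 excludes "Heart rate <45 bpm or >100 bpm based on vital signs assessment (rather than ECG"), so 45-59 bpm is eligible. Criterion 13 excludes "Systolic blood pressure ≥140 mmHg or diastolic blood pressure ≥90 mmHg" and gives no lower supine limit. The only other screen on a low value is criterion 15, which rests on judgement: "Any other abnormal safety findings unless, based on the investigator's judgment, the findings are not medically significant".

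The baseline needed for a condition is already defined for Part A in SAP 4.2.1: "The 12-lead ECG and vital sign measurements performed pre-dose on Day 1 of each period will serve as the period-specific baseline". Elsewhere the SAP does use baseline for abnormal values. In 5.9.4, "Laboratory values outside the normal range for each parameter will be identified using shift tables", from baseline or period baseline. In 5.9.6.2, absolute QTcF categories stand beside categories of increase from baseline.

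**The concern.** A limit that an eligible person may already breach does not distinguish a value that arose after dosing from one that was there before. Heart rate <60, diastolic <=60 and systolic <=90 are such limits. Respiratory rate and temperature also have no numeric entry bound. In Part A the same person appears under several treatments (SAP 5.1), so one participant with a low resting rate can be counted under up to three doses and under placebo.

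Vital signs belong to the primary safety endpoint. With about 6 active participants per dose in Part A and 8 in Part B, a high background leaves little room to see a dose-related rise in these rows.

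**Working it through.** The documents state no expected frequency for any of these limits, so there is no plan figure to reproduce. The check has two parts.

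**1. Table limits against entry limits**

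- Heart rate <45 and >100, systolic >=140 and diastolic >=90 are the same as the exclusion limits in Protocol 5.2.
- Heart rate <60 lies inside the eligible range of 45-100 bpm.
- Diastolic <=60 and systolic <=90 have no numeric entry bound.

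**2. Size of the drug-free background**

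Inputs from the documents:
- Group sizes: about 6 active of 8 per period in Part A (3:1, Protocol 4.1.1.1); 8 active of 10 per cohort in Part B (Protocol 4.1.2).
- Supine records after dosing in Part A: 8 per period (0.5, 1, 2, 4, 8, 12, 24 and 48 h; Protocol Table 1).
- Supine records after the first dose in Part B (Protocol Table 3 footnote on supine measurements, and Table 4): 7 after the Day 1 dose, 8 around the Day 14 dose, 2 x 2 on Days 4 and 7, and 13 other days to Day 17. The two 24 h readings fall on Days 2 and 15, so 7 + 8 + 4 + 13 - 2 = 30.

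Inputs assumed, not in the documents:
- Heart rate: mean 60-75 bpm, between-person SD 8-10, within-person SD 4-6.
- Diastolic: mean 65-75 mmHg, between-person SD 7-8, within-person SD 4-6.

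Model: reading = personal mean + within-person noise, both normal, with the entry limits applied and no drug effect. Systolic <=90 was not simulated. The table gives the range over the assumed inputs, as a share of participants.

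| Limit and part | Beyond limit at baseline | At least one counted record | Counted, baseline in range | Counted, and fall >=15 from baseline |
|---|---|---|---|---|
| HR <60, Part A | 4-45% | 12-80% | 9-38% | 0.5-16% |
| HR <60, Part B | 4-44% | 19-91% | 15-51% | 2-32% |
| Diastolic <=60, Part A | 4-33% | 12-68% | 9-37% | 0.6-14% |
| Diastolic <=60, Part B | 4-33% | 20-83% | 17-50% | 2-29% |

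The 15-unit fall is only an illustration of a change condition.

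Middle cases:
- Heart rate, mean 65, SDs 10 and 5: 0.539 x 6 = 3.2 of 6 active participants in Part A; 0.661 x 8 = 5.3 of 8 in Part B.
- Diastolic, mean 70, SDs 7 and 5: 0.384 x 6 = 2.3 of 6; 0.544 x 8 = 4.4 of 8.

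Chance that an active group has at least one counted participant: 1 - (1 - p)^n. At the lowest p this is 1 - (1 - 0.121)^6 = 0.54; at the highest it is about 1.

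Spread by chance at p = 0.54, n = 6: the probability of a count from 1 to 5 is 1 - 0.46^6 - 0.54^6 = 1 - 0.009 - 0.025 = 0.97. Almost any count is compatible with no drug effect.

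Share of counted participants already beyond the limit at baseline, Part A middle cases: heart rate (0.539 - 0.274) / 0.539 = 49%; diastolic (0.384 - 0.262) / 0.384 = 32%.

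Contrast with entry-matched limits (heart-rate mean 65, SDs 8 and 5): <45 is counted in about 5% (8 records) and 10% (30 records); >100 in about 0.05% and 0.13%.

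**The case against.** The strongest reply is that the plan already deals with baseline and background. Change from (period) baseline is in the same section. All vital-sign results are listed, so a flagged value can be read against its baseline. Placebo is pooled within each Part (SAP 5.1), which under the planned designs means about 2 x 8 = 16 placebo participants in Part A and up to 5 x 2 = 10 in Part B. Absolute-limit tables are also a pattern of this SAP: the liver categories in 5.9.4 and the absolute QTcF categories carry no baseline condition. The trial is descriptive, and this table is not named as an input to dose escalation.

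Much of this stands. It rules out saying that vital signs lack a baseline-referenced analysis. But the change summaries are group statistics by time point and do not show who newly crossed a limit. Pooled placebo shows the background without removing it, and the food-effect cohort takes no placebo at all. Listings leave the rule to be made after the data are seen. QTcF supports the concern as much as the reply, since its absolute categories are paired with change categories.

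A reader might infer three stronger things that the documents do not support:
- *That these rows will fill whatever the dose.* No resting distribution is given, and the assumed inputs span 12% to 91%. The four entry-matched limits are largely unaffected.
- *That most counted values were present before dosing.* For diastolic, people beyond the limit at baseline are a minority of those counted; within-person variation over many readings supplies the rest.
- *That the orthostatic definition is wrong.* The SAP says "Orthostatic change for blood pressure and heart rate is calculated as the difference in the standing value from the supine value" and then gives the formula explicitly as supine minus standing. That is a reproducible sign convention, and a positive fall agrees with defining orthostatic hypotension as a decrease.

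**Conclusion.** The point holds as a weakness of one descriptive table. For heart rate <60, diastolic <=60 and systolic <=90, the rule lets participants be counted with no change from their own baseline. Under the assumed inputs the drug-free share is 12-80% (Part A) and 19-91% (Part B) for heart rate <60, and 12-68% and 20-83% for diastolic <=60. The percentages depend on those assumptions; the absence of a baseline condition and the gap between table limits and entry limits come from the text alone. For systolic <=90 only the textual point is shown. No sample size, error rate or power is affected. The change is worth making because the table serves a primary safety endpoint and the data needed are already collected.

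**What to change.** In SAP 5.9.5:

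1. Keep the absolute-limit rows.
2. Beside each, show the number of participants already beyond that limit at baseline (period baseline in Part A).
3. Add a row for participants who are beyond the limit and also have a pre-stated change from (period) baseline, as 5.9.6.2 pairs absolute and change categories for QTcF. The trial team should choose the size of change before unblinding.
4. State that each participant is counted once per criterion within a treatment group, as 5.9.4 does for liver tests.

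An in-range-at-baseline condition should not replace the absolute rows. On its own it leaves heart rate <60 at 9-38% (Part A) and 15-51% (Part B). It would also hide a participant who goes from 58 to 46 bpm, whom the <45 row does not catch. That fall is 12 bpm, so a change row would show it only if the pre-stated change were 12 or less, which is a further reason to keep the absolute rows.

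The cost is SAP wording, one derived flag and a somewhat larger table. No new data are needed.

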### **5.9.6.     Electrocardiograms (ECGs)**

#### **5.9.6.1.    Continuous Electrocardiogram Recordings (Holter)**

Continuous ECGs readings and corresponding changes from period baseline, if Part A, or study baseline, if Part B, will be summarized by time point using descriptive statistics. The results of individual subjects at each timepoint will also be listed.

#### **5.9.6.2.    Standard 12-lead Electrocardiograms**

ECG parameters and corresponding changes from period baseline, if Part A, or study baseline, if Part B, will be summarized by time point using descriptive statistics. The results of individual subjects at each timepoint will also be listed.

The number and proportion of subjects having a worst post-baseline QTcF values from >450 msec to 480 msec, >480 msec to 500 msec, and >500 msec will be summarized. In addition, subjects with an increase from baseline of >30 msec to 60 msec and >60 msec will be summarized.

### **5.9.7.     Suicidal Ideation and Behavior Risk Monitoring**

The maximum post-baseline/post-period baseline results from the C-SSRS will be summarized by treatment. The maximum of each subscale (suicidal ideation [Categories 1-5], suicidal behavior [Categories 6-10], suicidal ideation or behavior [Categories 1-10], and self-injurious behavior without suicidal intent) will be presented. The number of patients with suicide-related treatment-emergent events, treatment-emergent suicidal ideation, and suicidal behavior, based on a comparison of the C-SSRS at baseline and/or previous lifetime experience to maximum C-SSRS scores across all post-baseline assessments will be provided for each treatment period.

All C-SSRS elements will be reflected in a listing.

### **5.10.     Pharmacokinetics**

The pharmacokinetic analysis is detailed in a separate PK Analysis Plan ([Appendix 9.5](#)).

### **5.11.     Protocol Deviations**

All protocol deviations will be reviewed by the project team prior to unblinding to identify subjects with important protocol deviations. Summaries of important deviations for the Safety Analysis Set will be presented by category and subcategory of deviation. All deviations from the protocol of the Safety Analysis Set will be listed by category along with a description and any additional comments.

### **5.12.     Timing of Analyses**

An interim database lock and analysis once Part A is complete may be conducted. Should the circumstance arise that the safety, tolerability, and pharmacokinetic data summary of completed cohorts are required for regulatory purpose, other interim analyses may also be conducted.

A final analysis will be conducted once the last subject completes or discontinues the study, the resulting clinical database has been cleaned and quality checked, the pre-analysis meeting has occurred, and the database has been locked.

## 6. CHANGES IN THE PLANNED ANALYSES

Should any deviations from the analyses specified in the authorized statistical analysis plan arise, such deviations will be documented in the final clinical study report.

## 7. REVISION HISTORY

Date	Revision	Rationale

## 9. APPENDICES

### 9.1. Schedule of Assessments

The Schedules of Assessments, as taken from the protocol, are provided in [Table 4](#) (Part A, SAD Cohorts 1 and 2), [Table 5](#) (Part A, Food Effect Cohort 3), and [Table 6](#) (Part B, MAD Cohorts 1-5).

**Table 4: Schedule of Assessments – Part A, Single Ascending Dose (Cohorts 1 and 2)**

Trial Periods/Phases	Screening		Treatment (In Clinic)												Follow-up a		
	Screening b	Initial Check-in b,c	Subsequent Check-ins b,c	Periods 1 to 4 d										Check-out/ET			
Day	-30 to -2	-1	-1	1					2					3			
Trial Hour				Predose e	0	0.5	1	2	3	4	6	8	12	16	24	36	48
Entrance and History																	
Informed consent	X																
Assign screening number	X																
Inclusion/exclusion criteria	X	X	X f														
Medical and psychiatric history g	←-----→			X g													
Demography	X																
History of drug and alcohol use	X																
Test for alcohol h	X	X	X														
Randomization				X i													
Safety Assessments																	
Height (Screening only) and weight	X	X	X														
Physical/neurological examination j	X	X	X												X		
Continuous ECG (telemetry)		X k															
Continuous ECG (Holter)				←-----X l -----→													

Trial Periods/Phases	Screening		Treatment (In Clinic)												Check-out/ET	Follow-up a	
	Screening b	Initial Check-in b,c	Subsequent Check-ins b,c	Periods 1 to 4 d													
Day	-30 to -2	-1	-1	1										2		3	
Trial Hour				Predose e	0	0.5	1	2	3	4	6	8	12	16	24	36	48
Standard 12-lead ECG m	X	X	X	X		X	X	X		X	X	X	X		X		X
Supine heart rate and blood pressure n	X	X	X	X		X	X	X		X	X	X	X		X		X
Standing heart rate and blood pressure o	X	X	X					X		X							
Respiratory rate and temperature	X	X	X	X											X		X
C-SSRS p	X	X	X														X
Prior/concomitant treatments q	←-----→																
Adverse event monitoring r			X r	X r	←-----→												
Laboratory																	
Blood for safety laboratory	X	X	X												X		X
Urine for safety laboratory	X	X	X												X		X
Urine drug screening s	X	X	X														
Hepatitis B, C, HIV	X																
FSH t	X																
PK blood sample				X u		X	X	X	X	X	X	X	X	X	X	X	
Blood sample for future biospecimen research v		X															
Other																	
Dosing					X												
Telephone contact																	X

Abbreviations: COVID-19=coronavirus disease-2019; C-SSRS=Columbia-Suicide Severity Rating Scale; [REDACTED] ECG=electrocardiogram; ET=early termination; FSH=follicle stimulating-hormone; IMP=investigational medicinal product; PK=pharmacokinetic; [REDACTED]

[REDACTED]

- a Contact with participant via phone call, internet/web, or other acceptable means of communication to check on their status 14±3 days after their final dose of IMP in the trial.
- b Participants must have COVID-19 testing done with a negative test result within a maximum of 5 days prior to, but as close as possible to, each admission to the clinic. COVID-19 testing may be performed after admission per the investigator's discretion.
- c Assessments can be completed at Check-in for all participants in the cohort (sentinel and non-sentinel) during each period. No additional Check-in assessments are required for non-sentinel participants provided that those participants remain domiciled under close observation and the Check-in assessments are performed within 48 hours prior to dosing.
- d There will be a washout period of at least 5 days between doses.
- e Predose assessments to be completed within 60 minutes of dosing unless otherwise noted.
- f Inclusion/exclusion criteria will be assessed at the start of each trial period to ensure ongoing participant eligibility with the exception of age or assessments that are only scheduled during Screening (eg, height).
- g Medical occurrences that begin before the start of IMP dosing but after obtaining informed consent will be recorded as medical and/or psychiatric history. This also applies to replacement participants.
- h An alcohol test (breathalyzer or blood/urine) is required at Screening and at Check-in for each period. The alcohol test may be conducted at any time during the trial at the discretion of the investigator.
- i Period 1 only.
- j Full physical and neurological examinations should be completed at Screening and Check-out of each period (or ET). A limited examination (cardiovascular, pulmonary, and gastrointestinal) should be completed at Check-in to clinic on Day -1 of each period. Symptom driven physical and/or neurological examinations may be done at any time point during the trial at the investigator's discretion.
- k A one-time baseline report of continuous ECG telemetry will be recorded for each participant by the site for a minimum of 12 hours starting on Day -1 prior to first dose. This baseline report will also be required for replacement participants.
- l Continuous ECG will be recorded for a minimum of 26 hours, starting at least 2 hours predose and continuing until 24 hours postdose. Electrocardiograms will be extracted from the continuous recording by a central ECG service from the following time points: -45, -30, and -15 minutes predose, and 0.5, 1, 2, 3, 4, 8, 12, and 24 hours postdose. Participants should be resting quietly in a supine position for at least 10 minutes before and 5 minutes after each extraction time point.
- m Triplicate ECGs will be obtained to confirm eligibility at Screening. Single ECGs will be obtained at all other time points.
- n Blood pressure and heart rate measurements will be obtained from participants in a supine position after at least 3 minutes of rest.
- o Orthostatic blood pressure and heart rate measurements will be obtained from participants in the standing position.
- p The "Baseline/Screening" C-SSRS form will be completed for all participants at Screening to determine eligibility. The "Since Last Visit" C-SSRS form will be completed at Check-in for each period to ensure that the participant continues to qualify for the trial and will also be completed at Check-out (or ET).
- q Concomitant medications should be recorded from Screening through the participant's last visit/contact.
- r Adverse events (serious and nonserious) will be recorded from first dose of IMP through the participant's last visit/contact. This also applies to replacement participants.
- s Additional urine drug screening can be conducted at any time during the trial at the discretion of the investigator.
- t A confirmatory FSH is required for all post-menopausal women.
- u Predose PK samples (1 sample and 1 backup sample) will be obtained within 15 minutes prior to dosing.
- v Future biospecimen research sample is optional and is only to be collected if signed consent is obtained from the participant. Sample can be collected at any time prior to initiation of first dose.

